Cover Page	1
Official Study Title:	2
Effect of Low-Dose Caffeine on Performance in Elite Sitting Volleyball Players	3
NCT Number:	4
NCT number pending	5
Date of Document:	6
June 28, 2025	7
	8
	9
	10
	11
	12
	13
	14
	15
	16
	17
	18
	19
	20
	21
	22
	23
	24
	25
	26
	27
	28
	29
	30
	31
	32
	33
	34
	35
	36

Materials and Methods

37

Participants

38

Thirteen elite male sitting volleyball players (29.84 ± 11.50 years) from the 2024 Paravolley European Champion Turkish Sitting Volleyball Men's National Team participated in this study. as the inclusion criteria were: (1) having a minimum level of disability according to the World ParaVolley classification, (2) not having any neuromuscular or musculoskeletal disorders that would prevent participation in the measurements, (3) not smoking or consuming alcohol, and (4) not using any ergogenic support to increase performance in the last 3 months. Exclusion criteria were: (1) failure to complete all test sessions, (2) occurrence of injury or illness during the study period that could affect performance and (3) changes in habitual caffeine consumption during the study.

45

All athletes were given detailed information about the study, their voluntary participation was ensured, and an informed consent form was obtained before any measurement. The study was approved by the Sinop University Human Research Ethics Committee (approval no: 2025/91) and was conducted in accordance with the ethical standards of the Declaration of Helsinki [19]. This study adheres to the Consolidated Standards of Reporting Trials (CONSORT) guidelines to ensure transparency and comprehensive reporting of the randomized controlled trial design and methodology (Figure 1).

50

[figure not shown]

Figure 1. CONSORT flowchart of the study

51

[figure not shown]
Study Design

52

[figure not shown]

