This study had a randomized, double-blind, counterbalanced, and cross-over design. Athletes participated in a total of three sessions (one familiarization session and two test sessions) (Figure 2). Participants were randomly divided into two groups ($n=7$ and $n=6$) using a computer-based random number generator (simple randomization, 1:1 ratio), one group receiving low-dose caffeine (L-CAF) and the other group receiving placebo (PLA) As required by the design, each participant received both supplements, but the order of supplementation was randomized. A 48-hour washout period was given between each test sessions. All measurements were performed at the same time interval (e.g., 09:00 - 10:00) to minimize the possible effects of circadian rhythm differences. Participants were asked not to change their eating habits, to avoid intense exercise, and to consume alcohol during the study. They were also advised to maintain their individual daily caffeine consumption habits. Moreover it taken all participants daily caffeine consumption survey before sessions.

53

54

**Figure 2.** Test Protocol

In each test session, participants consumed a randomly assigned supplement containing caffeine (LCAF) or placebo (PLA) with 250 ml of water 45 minutes before the tests. All participants completed a standard warm-up protocol which consisted of a 5-minute low-intensity general warm-up, followed by 10 minutes of dynamic stretching and technical work, 15 minutes before the test. After the warm-up period, athletes performed the serve speed, spike speed, and speed-endurance performance tests, respectively. In the serve and spike speed tests, each athlete performed three trials, and the highest value was recorded. Participants were given a 30-second rest period between trials and a 2-minute rest period between tests (Figure 3.). Rating of Perceived Exertion (RPE) during the speed-endurance course were recorded using the Borg 6-20 scale immediately at the end of the test. Caffeine and placebo doses were prepared using an analytical laboratory balance (Shimadzu, Tokyo, Japan) capable of measuring to within precision of 1 mg, and Oxford brand pure caffeine powder (ISO 14001; The Oxford Vitality Health Company Ltd; London, UK) and polydextrose was used throughout the study.

**Figure 3.** Timeline of Daily Experimental Procedures**Data Collection Tools***Serve Speed*

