All data are reported as mean \pm standard deviation (Mean \pm SD). Normality of distribution of data was assessed by Shapiro-Wilk normality test. Paired t-test was applied to examine the differences between LCAF and PLA conditions in serve speed, spike speed and speed-endurance performance. Power analysis was conducted using G*Power for a paired-samples t-test (two-tailed, $\alpha = 0.05$, $n = 13$, power = 0.80). Cohen's d coefficient was calculated for effect sizes and interpreted according to the following classification: insignificant (<0.2), small (0.2-0.5), medium (0.5-0.8) and large (>0.8) [20]. Statistical significance was accepted as $p < 0.05$. All analyses were performed using IBM SPSS Statistics 25.0 (IBM Corp., Armonk, NY, USA) software.

104

105

106

107

108

109

110

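### Each effect is graded from the point estimate of an unspecified Cohen's d in 13 players, with no confidence interval planned, so the grade will often be wrong

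*Combined protocol and SAP*

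**What the plan says.** The sample is "Thirteen elite male sitting volleyball players" in a two-condition crossover in which "each participant received both supplements, but the order of supplementation was randomized". The Data Analysis section sets out the reporting:

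- Descriptives: "All data are reported as mean" ± SD.
- Test: "Paired t-test was applied to examine the differences between LCAF and PLA conditions in serve speed, spike speed and speed-endurance performance".
- Decision: "Statistical significance was accepted as" p < 0.05.
- Magnitude: the Cohen's d "coefficient was calculated for effect sizes and interpreted according to the following classification: insignificant (<0.2), small (0.2-0.5), medium (0.5-0.8) and large (>0.8").

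The section does not tie d to each outcome in so many words. But d comes in the same paragraph as the three paired comparisons, so one grade per outcome is a fair reading. No section plans an interval for d or for the mean difference. None says whether d is standardised by the SD of the differences (dz) or by the SD of the scores (called raw-SD d here: mean difference over the root mean square of the two condition SDs). The paragraph shows no sign of redaction.

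**The concern.** The grade is the only interpretation of magnitude that the plan provides. It comes from cut-points 0.3 apart, applied to an estimate from 13 pairs. If the sampling error of d is several times the width of a band, the word reported says little about the true effect. A reader who sees *large* or *medium* has no interval to show how loosely it is supported. The unnamed standardiser adds to this: the same data can earn different words depending on a choice the plan leaves open.

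**Working it through.** **Inputs.** From the document: n = 13 pairs (df = 12), two-sided α = 0.05, cut-points 0.2, 0.5 and 0.8. Assumed: normally distributed differences and, for raw-SD d, equal SDs and a within-player correlation r between conditions, taken over 0 to 0.9 because no section gives it.

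**The plan's own figure.** The power statement gives n = 13 and power 0.80 but no effect size, so it cannot be reproduced as a check. Solving the noncentral t for 80% power gives dz = 0.847.

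**Grades on dz.** Observed dz = t/√13, and t is noncentral t with 12 df and noncentrality δ√13, where δ is the true dz. The cut-points on |t| are 0.2 × 3.606 = 0.721, 0.5 × 3.606 = 1.803 and 0.8 × 3.606 = 2.884. The probability of each grade is a difference of noncentral t distribution functions at these points, with both signs counted:

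| True dz | insignificant | small | medium | large |
|---|---|---|---|---|
| 0.35 | 26.5% | **41.4%** | 23.3% | 8.8% |
| 0.65 | 5.1% | 24.2% | **36.7%** | 34.0% |
| 1.0 | 0.2% | 4.0% | 20.7% | **75.1%** |

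At true 0.35 the effect is over-graded in 23.3 + 8.8 = 32.1% of trials. Over all true values in the medium band, the chance of being graded *medium* runs from 32.6% to 36.7%, with the maximum near 0.655. The best case in the small band is 41.9%. A Hedges small-sample correction raises the medium maximum only to 38.5%.

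**Significant results on dz.** The smallest significant dz is 2.179/3.606 = 0.604. A truly small effect that reaches p < 0.05 can therefore never be graded *small*. At true 0.65, power is 57.7%. The share of significant results graded *large* is 0.340/0.577 = 58.9%, which leaves 41.1% graded *medium*.

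**Interval width on dz** (noncentral t inversion):

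| p | 95% CI of dz | Width |
|---|---|---|
| 0.05 | 0.00 to 1.19 | 1.19 |
| 0.037 | 0.04 to 1.24 | 1.20 |
| 0.01 | 0.196 to 1.47 | 1.28 |

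The small and medium bands are 0.3 wide.

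**Grades on raw-SD d.** These come from simulated trials of 13 bivariate-normal pairs, at least 100,000 per setting. The last row uses raw-SD d = dz × √(2(1 − r)) at p = 0.01.

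| Assumed r | 0 | 0.3 | 0.5 | 0.7 | 0.8 | 0.9 |
|---|---|---|---|---|---|---|
| True 0.35 graded correctly | 36% | 39% | 42% | 50% | 57% | 70% |
| True 0.65 graded correctly | 29% | 33% | 38% | 46% | 51% | 60% |
| d at p = 0.01 (95% CI) | 1.20 (0.28–2.08) | 1.00 (0.23–1.74) | 0.85 (0.20–1.47) | 0.66 (0.15–1.14) | 0.54 (0.12–0.93) | 0.38 (0.09–0.66) |

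The same p = 0.01 is *large* on dz (0.85), but on raw-SD d it runs from *large* at r = 0.5 to *small* at r = 0.9.

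**How many grades the raw-SD interval covers.** Take r = 0.9 in the population and results with p between 0.005 and 0.05. The interval covers three or more grades in about 82% of them when the true d is 0.35, and in about 49% when there is no effect. Over all results with no effect at r = 0.9, about 87% of intervals cover two grades or fewer.

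**The case against.** The strongest reply is that nothing decisive hangs on the grade. It sits beside Mean ± SD and a p-value, and no section makes it a headline, a decision rule or the basis of a conclusion. Loose labels follow from any study of 13 using conventional bands. All of that stands, and it limits the point to how magnitude is reported.

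Four stronger readings are tempting, and the documents do not support them:

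- *The 37% applies to the plan's d.* It applies to dz, and the plan does not name dz. On raw-SD d a true 0.65 is graded correctly in 46–60% of trials if r is 0.7 to 0.9.
- *Grading is worse among significant results in general.* This holds only for truly small effects. At true dz 0.65, correct grading rises from 36.7% overall to 41.1% among significant results, and at true dz 1.0 from 75.1% to 82.4%.
- *The interval always spans three or four grades.* On raw-SD d this depends on r and often fails when r is near 0.9, as shown above.
- *Raw-SD d is the right choice.* That is partly preference. It can be checked from the planned Mean ± SD, whereas dz at fixed n only restates p (*large* is p < 0.0137, *medium* is p from 0.0137 to 0.097). Either is acceptable if it is named and given with its interval.

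**Conclusion.** The point holds in a limited form, as a cheap improvement. Followed as written, the rule attaches to each outcome a word that is often wrong, and it gives no interval to warn the reader. On dz, correct grading is 41% at true 0.35 and at most 37% for a true medium effect, with true 0.65 called *large* in 34% of trials. On raw-SD d it is about 36–70% at true 0.35 and 29–60% at true 0.65. The dz figures need only n = 13 and normal differences. The raw-SD figures also rest on the assumed r and on equal SDs. A reader might infer that the trial's significance findings are unsound. They are not touched: neither the paired t-test nor the p < 0.05 decision uses d.

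**What to change.** Replace the grading sentence in Data Analysis. For each of the three outcomes:

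1. Report the mean difference (LCAF minus PLA) in original units with its 95% CI.
2. Name the standardiser used for d and report d with its 95% CI.
3. Base the interpretation of magnitude on the grades that interval covers, not on the label of the point estimate alone.

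In the cases tabulated above, the range of grades covered by the interval contains the true grade in 98% or more of trials. A p = 0.01 result on dz would then be reported as compatible with effects from about 0.2 to 1.5, not simply as *large*.

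The cost is one sentence and two results columns, from data already collected, with no change to the test or the sample. The drawback is that many results, especially at low to moderate r, will be compatible with several grades, so a one-word effect size can no longer be claimed.

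### Cohen's d from 13 athletes, with no stated small-sample correction and no named standardiser, overstates the standardised effect by about 4–7% on average; name the standardiser and report Hedges' g with a 95% interval

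*Combined protocol and SAP*

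**What the plan says.** The Participants section gives the sample: "Thirteen elite male sitting volleyball players". Under Study Design, "each participant received both supplements, but the order of supplementation was randomized", so each athlete supplies one caffeine-minus-placebo difference per outcome. Data Analysis compares the conditions by paired t-test for serve speed, spike speed and the speed-endurance test. It then says that Cohen's d "coefficient was calculated for effect sizes and interpreted according to the following classification", with the grades "insignificant (<0.2), small (0.2-0.5), medium (0.5-0.8) and large (>0.8".

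Three things are not stated: the SD that forms the denominator of d, any small-sample correction, and a confidence interval for d. The documents contain no results.

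**The concern.** Cohen's d divides a mean difference by an SD estimated from few observations. Small-sample SDs vary, and dividing by them inflates the expected value of the ratio. At 12 degrees of freedom the inflation is no longer negligible. It also runs in one direction, away from zero, so pooling several such estimates would not average it out. The plan then turns d into a verbal grade, which makes d the figure that readers will carry away.

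At stake is the accuracy of the reported effect sizes. No significance decision depends on it.

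**Working it through.** **Plan's own figure.** The documents give no value of d and no bias figure to reproduce. The nearest figure is the power statement (n = 13, two-tailed 5% level, power 0.80), which names no effect size and so cannot be checked. Solving the noncentral t for it gives a standardised paired difference (dz) of 0.847.

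**Inputs.** From the documents: n = 13 and grade limits of 0.2, 0.5 and 0.8. Assumed: normal differences, and a within-athlete correlation r wherever the denominator is a between-athlete SD.

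**Case A: SD of the paired differences (dz), df = 13 − 1 = 12.**
- Correction factor: J(df) = Γ(df/2) / [√(df/2) · Γ((df−1)/2)].
- J(12) = Γ(6) / [√6 · Γ(5.5)] = 120 / (2.449 × 52.34) = 0.936.
- Mean of d = true value / J, and 1/0.9359 = 1.068, an overstatement of 6.8%.
- True 0.50 averages 0.50 × 1.0684 = 0.534; true 0.80 averages 0.855. Simulation agrees (about 0.535 and 0.855).

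**Case B: average SD of the two conditions.** The effective df is about 24/(1 + r²).

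| Assumed r | df | Overstatement |
|---|---|---|
| 0 | 24.0 | 3.3% |
| 0.5 | 19.2 | 4.1% |
| 0.7 | 16.1 | 5.0% |
| 0.9 | 13.3 | 6.1% |
| 0.95 | 12.6 | 6.5% |

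Simulation agrees with these to within about 0.4 percentage points.

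**Size against noise (dz, true 0.5).**
- E(dz²) = (12/10) × (1/13 + 0.25) = 0.3923.
- Sampling SD = √(0.3923 − 0.5342²) = 0.327. The bias of 0.034 is 0.034/0.327, about a tenth of one SD.
- RMSE of d = √(0.3923 − 2 × 0.5 × 0.5342 + 0.25) = 0.329.
- RMSE of g = √(0.9359² × 0.3923 − 0.25) = 0.306, which is 7% lower.
- The bias is proportional to the true effect: zero at 0 and about 0.014 at 0.2.

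**Interval for the effect size.** Set t = d√13 on 12 df, invert the noncentral t for the 95% limits, and divide by √13. An observed dz of 0.5 gives −0.09 to 1.07, and 0.8 gives 0.16 to 1.42. Both intervals reach all four grades.

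**Why the standardiser comes first.** With equal SDs in the two conditions, the SD of the differences is √(2(1 − r)) times the condition SD. At r = 0.5 the factor is 1. At r = 0.9 it is √0.2 = 0.447, so the same data give a dz of 1/0.447 = 2.2 times the average-SD version. That ambiguity is far larger than the 4–7% bias.

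**The case against.** The best case against acting has four parts.

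1. **The harm to grading does not follow.** A reader might infer that the bias pushes borderline outcomes up, so that an observed dz of 0.200–0.214, 0.500–0.534 or 0.800–0.855 is graded one class too high. The documents do not support this. They contain no results, and a bias in the mean does not make each estimate in a band too high. Uncorrected dz is nearly median-unbiased: at a true 0.5 its median is 0.511, against 0.478 for g. If true effects are assumed uniform on 0–1.2, the true value lies at or above the cut-off in about 67% and 55% of trials landing in the lower two bands, and in just under half for the top band. Whether correction improves grading depends on the assumed effects: the share of correct grades goes from 40.4% to 42.3% for true effects uniform on 0–0.8, but from 51.5% to 50.9% on 0–1.2. This objection stands.
2. **The absence of correction is inferred.** The text neither states nor rules one out. That is true, but a plan that names Cohen's d and mentions no correction is ordinarily read as using none.
3. **The bias is small beside sampling error, and Cohen's d is conventional.** Both are true, and both limit the weight of the point. They do not remove a one-directional bias, and here correction lowers RMSE as well as bias.
4. **No inference changes.** This stands in full: p-values and significance decisions are the same with or without correction.

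**Conclusion.** The point holds as a minor reporting refinement. On the ordinary reading that no correction is applied, d overstates the true standardised effect on average by 6.8% if the SD of the paired differences is the denominator. With an average SD the excess is about 4–6.5% for r between 0.5 and 0.95 (3.3% if r were 0). These figures assume normal data, and those for the average SD also rest on assumed correlations that the documents do not give.

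The finding goes no further than a mean bias. It does not show that any outcome will be misgraded, that grades would be more accurate after correction, or that the t-tests are affected. The unnamed standardiser and the missing interval matter more to a reader than the correction factor does, and the correction cannot be chosen until the standardiser is named.

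**What to change.** In Data Analysis:

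- State which SD standardises d.
- Report Hedges' g with the correction that matches that choice. For the SD of the paired differences, multiply dz by 0.936. For an average SD, use the paired-design factor with df of about 24/(1 + r²), where r is the observed correlation.
- Give a 95% confidence interval for each effect size and treat the verbal grade as secondary, since at n = 13 the interval spans several grades.

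**Cost.** No new data, one multiplication and one interval per outcome, and a sentence or two of text. Reported effects become about 6% smaller (1 − 0.936 = 6.4% for dz). If the existing cut-offs are kept, truly large effects are labelled 'large' less often: 69% of trials against 75% at a true dz of 1.0, and 46% against 52% at 0.8. In exchange the mean bias is removed, and RMSE at a true 0.5 falls from 0.329 to 0.306.
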